7 PROCEDURES FOR REPORTING ADVERSE EVENTS

7.1 Adverse Events Definitions

The investigator will monitor the occurrence of AEs during the course of the study that will end with Visit 4.

The following definitions of terms are guided by the United States Code of Federal Regulations (21 CFR 312.32(a)) and are included here.

Adverse event is any untoward medical occurrence in a patient associated with the use of a drug in humans, whether or not considered drug related.

Suspected adverse reaction means any adverse event for which there is a reasonable possibility that the drug caused the adverse event. For the purposes of IND safety reporting, "reasonable possibility" means there is evidence to suggest a causal relationship between the drug and the adverse event. Suspected adverse reaction implies a lesser degree of certainty about causality than adverse reaction, which means any adverse event caused by a drug.

Unexpected adverse event (adverse drug experience) or (suspected) adverse reaction means any adverse event or (suspected) adverse reaction that is not listed in the investigator brochure or is not listed at the specificity or severity that has been observed.

An AE or suspected adverse reaction is considered "serious" if, in the view of either the investigator or sponsor, it results in any of the following outcomes: Death, a life-threatening adverse event, inpatient hospitalization or prolongation of existing hospitalization, a persistent or significant incapacity or substantial disruption of the ability to conduct normal life functions, or a congenital anomaly/birth defect. Important medical events that may not result in death, be life-threatening, or require hospitalization may be considered serious when, based upon appropriate medical judgment, they may jeopardize the patient and may require medical or surgical intervention to prevent one of the outcomes listed in this definition.

An adverse event is considered "life-threatening" if, in the view of either the investigator or sponsor, its occurrence places the patient at immediate risk of death. It does not include an adverse event that, had it occurred in a more severe form, might have caused death.

Suspected Unexpected Serious Adverse Reaction (SUSAR) is any (suspected) adverse reaction (any adverse event for which there is a reasonable possibility that the drug caused the adverse event) that is both serious and unexpected.

An adverse device effect (ADE) is defined as any untoward and unintended response to a medical device, in this study, the camera/imaging system. This definition includes any adverse event resulting from insufficiencies or inadequacies in the instructions for use or the deployment of the device, as well as any adverse event that is the result of a user error [ISO 14155-1:2003 (E) 3.1].

All ADEs noted during the study will be reported in the eCRF.

A suspected ADE is a subset of all ADEs for which there is a reasonable possibility (ie, evidence to suggest a causal relationship between the device and the ADE) that the device caused the event. Suspected ADE implies a lesser degree of certainty about causality than adverse device effect.

An unanticipated ADE is any serious adverse effect on health or safety or any life-threatening problem or death caused by, or associated with, a device, if that effect, problem, or death was not previously identified in nature, severity, or degree of incidence in the investigational plan or application, or any other unanticipated serious problem associated with a device that relates to the rights, safety, or welfare of subjects. [21 CFR 812.3 (s)]

7.2 Reporting of Adverse Events

7.2.1 Adverse Events

The safety of all patients enrolled in this study will be recorded from the time of study drug administration and throughout the course of the study that will end with Visit 4.

All AEs (including ADEs) will be recorded in the appropriate section of the eCRF. Patients withdrawn from the study because of AEs will be followed by the investigator until the outcome is determined. When appropriate, additional written reports and documentation will be provided.

All AEs (including ADEs) beginning after the exposure to study drug must be reported to the sponsor or its designee if the onset of the AE was before Visit 4. All AEs (including ADEs) that are judged by the investigator to be not related to study drug need not be reported to the sponsor or its designee after Visit 4. All AEs (including ADEs) that are judged by the Investigator to be at least possibly related to study drug administration must be reported to the sponsor or its designee regardless of how much time has elapsed since the last exposure to study drug.

7.2.2 Laboratory Abnormalities

To the extent possible, all laboratory abnormalities observed during the course of the study will be included under a reported AE describing a clinical syndrome (e.g., elevated blood urea nitrogen and creatinine in the setting of an AE of “renal failure” or elevated ALT/AST in the setting of an AE of “hepatitis”). In these cases (e.g., an AE of renal failure), the laboratory abnormality itself (e.g., elevated creatinine) does not need to be recorded as an AE.

In the absence of a reported AE identifying a clinical syndrome that encompasses the observed laboratory abnormality that “isolated” laboratory abnormality itself should be reported as an AE.

Patients experiencing AEs or laboratory abnormalities will be assessed and appropriate evaluations and interventions performed until all parameters have returned to baseline levels, or are consistent with the patient’s then-current physical condition, in the opinion of the investigator.

7.2.3 Serious Adverse Events

Instructions for reporting Serious Adverse Events (SAE) and Suspected Unexpected Serious Adverse Reactions (SUSAR) are found on [Page 2](#). A written report of all SAEs that occur after the administration of study drug and during the study (ending with Visit 4) must be submitted to the IRB/ethics committee (EC) and the Sponsor. SAEs/SUSARs must be reported to the Sponsor within 24 hours for a determination of expedited reporting to FDA, as described in [Section 7.5](#)

below. In all SAE reports, the investigator will advise whether or not the SAE is judged to be related to study drug administration. SAEs that occur after Visit 4 and are not reasonably associated with study drug do not require reporting per the instructions given below. All SAEs that are judged by the investigator to be at least possibly related to study drug administration must be reported to the sponsor or its designee regardless of how much time has elapsed since the last exposure to study drug. All AEs must be submitted to the IRB/EC in an annual report.

7.2.4 Reporting of Pregnancies

If a patient becomes pregnant during the course of the study, the investigator or site personnel must notify the Medical monitor (see [Page 3](#) for details) within 5 working days after the investigator or site personnel become aware of the pregnancy. If an SAE occurs in conjunction with the pregnancy, then the reporting time frame for an SAE must be met.

7.2.5 Disease Progression

The progression of the ovarian cancer per se will not constitute an AE. However, if the progression of the ovarian cancer meets the criteria for an SAE, then it should be reported as an SAE (see [Page 2](#)).

7.2.6 Overdoses

Overdoses should be reported as a protocol violation. If an overdose results in an AE, the CRF AE page should be completed, and source documents included. If the overdose results in an SAE, then SAE reporting should be followed using the specific CRF pages with overdose information entered in the narrative section. All available clinical information relevant to overdose, including signs and symptoms, laboratory findings, and therapeutic measures or treatments administered, should be summarized and discussed.

7.3 Classification of Adverse Events by Severity

The investigator must categorize the severity of each AE according to the following:

- Mild: Awareness of signs or symptoms, but easily tolerated and are of minor irritant type. Symptoms do not require therapy or a medical evaluation; signs and symptoms are transient.
- Moderate: Events introduce a low level of inconvenience or concern to the participant, but are usually improved by simple therapeutic measures; moderate experiences may cause some interference with functioning
- Severe: Events generally require systemic drug therapy or other treatment; they are usually incapacitating

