
Eligibility Criteria
	
Inclusion:
 
 1. Female patients 18 years of age and older 2. Have a primary diagnosis, or at high clinical suspicion, of primary ovarian cancer (of epithelial type), planned for primary surgical cytoreduction, interval debulking, or have recurrent ovarian cancer surgery, and: 
 o Who are scheduled to undergo laparotomy for the debulking surgery OR o Who are scheduled to undergo laparoscopy and pre-authorized to undergo laparotomy for the debulking surgery if cancer is detected on the laparoscopy 3. A negative serum pregnancy test at Screening followed by a negative urine pregnancy test on the day of surgery or day of admission for female patients of childbearing potential 4. Female patients of childbearing potential or less than 2 years postmenopausal agree to use an acceptable form of contraception from the time of signing informed consent until 30 days after study completion 5. Ability to understand the requirements of the study, provide written informed consent for participation in the study and authorization of use and disclosure of protected health information, and agree to abide by the study restrictions and to return for the required assessments 
Exclusion:
 
 1. Previous exposure to OTL38 2. Known FR-negative ovarian cancer 3. Planned surgical debulking via laparoscopy or robotic surgery, with no intent of laparotomy. 4. Patients with known ovarian cancer miliary disease determined pre-operatively to be inoperable. 5. Any medical condition that, in the opinion of the investigators, could potentially jeopardize the safety of the patient 6. History of anaphylactic reactions 7. History of allergy to any of the components of OTL38, including folic acid 8. Pregnancy or positive pregnancy test 9. Clinically significant abnormalities on electrocardiogram (ECG) 10. Presence of any psychological, familial, sociological or geographical condition potentially hampering compliance with the study protocol and follow-up schedule 11. Impaired renal function defined as eGFR < 50 mL/min/1.73m² 12. Impaired liver function defined as values > 3x the upper limit of normal (ULN) for alanine aminotransferase (ALT), aspartate aminotransferase (AST), alkaline phosphatase (ALP), or total bilirubin. 13. Known Stage IV ovarian cancer with brain metastases 14. Received an investigational agent in another clinical trial within 30 days prior to surgery 15. Known sensitivity to fluorescent light

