14.3 Adverse Events

Adverse events occurring prior to exposure to OTL38 administration will be provided in line listings. Treatment emergent adverse events (TEAEs) will be summarized via the Medical Dictionary for Regulatory Activities (MedDRA) system organ class and preferred term using patient incidence rates. Data will be tabulated by severity, physician assessment of relationship to study drug, serious TEAEs, and TEAEs leading to death or early study withdrawal. Further description of TEAEs may be defined by temporal onset to study drug infusion. Additional summaries of TEAEs identified as potential ADEs will also be provided.

Treatment-emergent AEs will be summarized for all patients in the safety analysis set. Summary tables will reflect the number and percent of patients experiencing at least 1 TEAE in each system organ class and preferred term. The overall number and percent of patients experiencing any treatment-emergent AE will also be provided. All percentages will use the number of patients in the safety analysis set as the denominator. An exception will be the presentation of ADEs which will use all patients undergoing fluorescent light imaging as the denominator. If a patient has more than one AE within a system organ class, the patient will be counted only once in that system organ class. If a patient has more than 1 AE that codes to the same preferred term, the patient will be counted only once for that preferred term. The tabular summary will be sorted by descending order of overall incidence.

Treatment-emergent AEs will also be summarized by the maximum relationship to study drug as determined by the Principal Investigator as well as the maximum severity of the event. Relationship to drug will be scored as Definite, Probable, Possible, or Not Related. Related AEs will be classified as those scored as Definite, Probable, and Possible. Severity will be rated as Mild, Moderate, or Severe. If a patient experiences more than 1 AE within system organ class or preferred term, that patient will be counted only once for that event under the maximum severity or most related category within the relevant category. In the event that the relationship to study drug or the severity of the event is missing, for tabulation purposes the maximum relationship or severity will be assumed.

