14.5 Clinical Laboratory Evaluations

The analysis of laboratory parameters will include descriptive statistics for the change from baseline to each post-baseline study visit as well as shifts from baseline to each post-baseline study visit for categorical lab parameters. In addition, shift tables (i.e., low-normal-high at baseline versus low-normal-high at last visit) will be provided. Urinalysis and pregnancy results will not be summarized but will be provided in a data listing. For all relevant laboratory data, values above or below normal limits will be flagged along with the direction of abnormality in line listings.

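### The adverse event severity scale does not grade laboratory abnormalities by size, and the planned low-normal-high shift tables do not fill the gap.

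*Protocol*

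**What the plan says.** Protocol 7.3 introduces its scale with "The investigator must categorize the severity of each AE according to the following". The grades are:

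- Mild: "Awareness of signs or symptoms, but easily tolerated and are of minor irritant type". The event is also transient and needs neither therapy nor medical evaluation.
- Moderate: "Events introduce a low level of inconvenience or concern to the participant, but are usually improved by simple therapeutic measures". Some interference with functioning is possible.
- Severe: "Severe: Events generally require systemic drug therapy or other treatment; they are usually incapacitating".

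Protocol 5.1.2 repeats the same three definitions.

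Protocol 7.2.2 asks that a laboratory abnormality be reported, where possible, under an AE that names a clinical syndrome. If no such AE covers it, the abnormality is itself reported as an AE. No size or clinical-significance threshold is given.

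SAP 14.3 summarises treatment-emergent AEs by strongest relationship to study drug "as well as the maximum severity of the event". It uses the same three levels and counts a missing severity as the maximum. Line listings do not carry that imputation.

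For laboratory data, SAP 14.5 plans descriptive statistics for change from baseline and listings that flag values outside normal limits. It adds that "shift tables (i.e., low-normal-high at baseline versus low-normal-high at last visit) will be provided".

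Numeric limits appear only at entry. Protocol 5.2.2 excludes patients with eGFR below 50 mL/min/1.73m² or with ALT, AST, ALP or total bilirubin above 3x ULN.

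**The concern.** The plan creates a class of AE, the isolated laboratory abnormality, and requires a grade for it on a scale with no laboratory criterion. If the patient feels nothing and no treatment is given, the grade depends on how each investigator at up to 16 sites stretches the wording. A marked hepatic or renal change and a trivial one can then share a grade. One left ungraded is tabulated as Severe.

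At stake is the reading of post-dose laboratory safety in a trial whose SAP describes a single arm with no comparator. Inconsistent grading cannot be offset against a control group. If the laboratory tables also fail to separate marked from slight changes, no output in the SAP text counts the patients who had a marked change.

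**Working it through.** The plan gives no figure to reproduce, so the check sets the definitions beside the events they must cover and then follows the result into the tables.

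**Step 1. Which events need a grade.** Under 7.2.2, an abnormality not covered by a syndrome AE is an AE. Under 7.3, each AE gets a grade. Every isolated abnormality must therefore be graded, whatever its size.

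**Step 2. Apply each grade to an untreated, asymptomatic abnormality.**

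- Mild turns on awareness and tolerability. Its mention of signs might be stretched to a laboratory finding, but that would cover a small and a large deviation equally. It also presumes that no medical evaluation is needed, whereas 7.2.2 has laboratory abnormalities assessed until they return to baseline or fit the patient's condition.
- Moderate turns on inconvenience or concern to the participant and on simple measures that help.
- Severe turns on treatment and incapacity.

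None contains a laboratory value, so size does not decide the grade.

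**Step 3. Follow the grade into SAP 14.3.** If the investigator calls a large rise Mild because the patient noticed nothing, it is tabulated as Mild. If the investigator leaves a trivial rise ungraded, it is tabulated as Severe, while the listing shows no grade. The error can run in either direction.

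**Step 4. Check whether SAP 14.5 recovers the size.** Let b = baseline value / ULN and w = post-dose value / ULN. A value is high when the ratio exceeds 1, and a patient is eligible on liver values when b ≤ 3. Every patient with 1 < b ≤ 3 and w > 1 falls in the high-to-high cell, however large w is.

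Illustration for ALT, with an assumed ULN of 40 U/L (entry limit 3 × 40 = 120 U/L):

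| Change in ALT (U/L) | b | w | Shift cell | Crosses 3x ULN |
|---|---|---|---|---|
| 100 to 800 | 100/40 = 2.5 | 800/40 = 20 | high to high | yes |
| normal to 41 | at most 1 | 41/40 = 1.025 | normal to high | no |
| normal to 800 | at most 1 | 800/40 = 20 | normal to high | yes |

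The largest relative rise among patients already high at entry registers as no shift. A rise to 1.025x ULN registers as one and shares its cell with a rise to 20x.

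The first row does not depend closely on the assumed ULN. A baseline of 100 is both high and eligible for any ULN from 100/3 = 33.3 up to just under 100 U/L. Over that range w runs from 800/33.3 = 24 down to just above 8. The second row holds at any ULN if 41 is replaced by 1.025 × ULN.

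**Step 5. Check the data.** Chemistries are taken at screening (5.7.1.1) and clinical laboratory tests at Visit 3, Day 7 ± 4 (5.7.1.3). A grade-based shift and a count of limit crossings need no new sampling, provided the Visit 3 panel includes the liver tests and creatinine. That is an assumption, since the panel is not itemised in the text shown.

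The documents give no rate for isolated laboratory AEs, so the number of patients affected cannot be computed.

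**The case against.** The case for leaving the plan alone has real substance.

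- **Syndrome rule first.** Protocol 7.2.2 moves abnormalities under a syndrome AE where it can, with renal failure and hepatitis as its examples. A very high ALT stays isolated only if no syndrome is diagnosed.
- **Size enters indirectly.** An abnormality that needs treatment can be placed in Moderate or Severe, so a reader who infers that laboratory AEs fit no grade at all goes too far. The gap is confined to untreated, asymptomatic abnormalities.
- **Other outputs rank harm.** SAP 14.4 tabulates serious, fatal and withdrawal events separately. Under the SAP 7 conventions, continuous summaries give minimum and maximum, and SAP 14.5 flags abnormal values in listings. With a minimum of 100 evaluable patients, a value of 800 would be noticed. The inference that the severity table cannot rank harm at all is not supported, because symptomatic events are still ordered.
- **Little hangs on the grade.** Safety analysis is descriptive, expedited reporting turns on seriousness and expectedness, and no visible rule or test uses severity.
- **Unseen shells.** SAP 1 places draft tables in a separate document, so what is missing is established only for the SAP text.

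A reader might also infer that receipt of any systemic drug makes an event Severe, so that routinely treated peri-operative events inflate that grade. The text does not say so. It speaks of what events generally require, not what was given, and pairs this with usual incapacity. Read together, a treated but non-incapacitating event sits more naturally in Moderate. What remains is an ambiguity: the protocol does not say whether both clauses must be met.

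These points narrow the concern without removing it. Extremes and listings show that a marked value occurred but do not count patients, and the seriousness tables do not grade non-serious laboratory AEs.

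**Conclusion.** The point holds for untreated, asymptomatic laboratory AEs. Protocol 7.3 and 5.1.2 give no criterion tied to the size of the abnormality, SAP 14.3 counts ungraded events at the maximum, and the three-category shifts in SAP 14.5 do not separate slight from marked change. For these events the severity table is unreliable in both directions.

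The effect is limited to descriptive safety reporting. The primary efficacy conclusion is untouched, and the frequency of such events is unknown from the documents. The overlap between Moderate and Severe needs only clarification. The conclusion rests on the visible text of 7.2.2, 7.3 and SAP 14.3 to 14.5, and on the separate table shells adding no graded laboratory output. The change is worth making because it is cheap and uses data the trial already collects.

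**What to change.** **SAP 14.5.** Add two programmed outputs:

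1. A shift table by numeric laboratory grade on a named scale, such as CTCAE, from baseline to worst post-dose value.
2. The number of patients who move from within to beyond the protocol's own entry limits: ALT, AST, ALP or total bilirubin above 3x ULN, and eGFR below 50 mL/min/1.73m². Here the limits serve only as reporting thresholds.

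**Protocol 7.3 and 5.1.2, in identical words.** State that isolated laboratory AEs are graded by the same numeric limits, and give the mapping to Mild, Moderate and Severe. The mapping is needed because the SAP has only these three levels. The investigator can still assign the AE grade, using those limits.

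**SAP 14.3.** Report how many severities in the table were imputed.

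**Secondary clarification in 7.3 and 5.1.2.** Say whether both clauses of Severe must be met, and how the treatment clause differs from the one in Moderate.

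The cost is a wording change in two sections and a few tables from existing data. Laboratory and symptomatic AEs will carry grades derived in different ways, which needs a footnote. Without a comparator, laboratory changes after surgery cannot be attributed to the drug from these counts alone, and the report should say so.

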7.4 Classification of Adverse Events by Relationship to Study Drug Administration

The relationship of each AE to the study drug administration or TEAE will be assessed by the investigator; after careful consideration, according to the following guidelines:

Definitely Related: An adverse event that has a timely relationship to the administration of the study drug and follows a known pattern of response for which no alternative cause is present

Probably Related: An adverse event that has a timely relationship to the administration of the study drug and follows a known pattern of response, but for which a potential alternative cause may be present

Possibly Related: An adverse event that has a timely relationship to the administration of the study drug, follows no known pattern of response, but a potential alternative cause does not exist

Not related: An adverse event for which there is evidence that it is definitely related to a cause other than the study; in general, no timely relationship to the administration of the drug exists, or if so, the event does not follow a pattern of response and an alternative cause is present

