5.4 Patient Discontinuation Criteria

Although a single dose of study drug is infused on Day 1, a patient may be withdrawn from the study for any of the following reasons:

- Request of the patient or patient's representative
- AEs or adverse device effects (ADEs) based on the judgment of the Investigator
- The Investigator decides that it is in the patient's best interest
- The patient is noncompliant with the protocol
- Lost to safety assessments during Visits 3 and 4 ([REDACTED])
- Death
- Other

If a subject is withdrawn at any time, the reason(s) will be recorded on the relevant page of the eCRF.

Patients discontinued due to AEs or ADEs will be monitored until resolution or stability of the event based on the judgment of the investigator.

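### Protocol 7.4 gives no related category to a timely event with no known pattern and a potential but unproven alternative cause, so the related-TEAE table can be wrong in either direction

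*Protocol*

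**What the plan says.** Protocol 7.4 defines four levels of relationship by three features: timing, pattern of response and alternative cause.

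- Definitely Related: timely, known pattern, no alternative cause.
- Probably Related: timely, and the event "follows a known pattern of response, but for which a potential alternative cause may be present".
- Possibly Related: timely, and the event "follows no known pattern of response, but a potential alternative cause does not exist".
- Not related: the opening clause reads "An adverse event for which there is evidence that it is definitely related to a cause other than the study". A second clause, introduced as a general description, adds that "no timely relationship to the administration of the drug exists", or, if the event is timely, that "the event does not follow a pattern of response and an alternative cause is present".

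The section calls these definitions guidelines, to be applied with the investigator's judgement.

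SAP 14.3 uses the same four levels. It counts Definite, Probable and Possible as related, summarises TEAEs by maximum relationship, and tabulates a missing relationship at the maximum. Protocol 8.2.6.1 also tabulates TEAEs by the physician's relationship score. Under Protocol 7.2.1 and 7.2.3, AEs and SAEs after Visit 4 must reach the sponsor if judged possibly related or stronger; those judged unrelated need not.

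**The concern.** The scale is inverted on one feature: the weakest related level is stricter about alternative causes than the level above it. A reaction not seen before has no known pattern, so Possibly Related is its only route to a related score. That route closes as soon as another cause is conceivable.

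Here another cause is often conceivable. Protocol 5.4 says "Although a single dose of study drug is infused on Day 1", and Protocol 5.1 makes Day 1 the day of surgery. Once the operation has begun, surgery is commonly a candidate cause.

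Attribution also carries more weight than usual. Safety is a secondary objective (Protocol 4.2). SAP 5 states that there is no comparator group and that all participants are expected to receive OTL38; the group randomised to no fluorescent imaging is dosed too. No undosed group exists to show an excess of events.

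The wording can also sit badly with Protocol 7.1, which says "Suspected adverse reaction means any adverse event for which there is a reasonable possibility that the drug caused the adverse event" and explains that a reasonable possibility "means there is evidence to suggest a causal relationship between the drug and the adverse event". That test does not require other causes to be absent, so an event could pass it and still be scored Not related under 7.4.

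**Working it through.** There is no figure in the plan to reproduce, so the check is on the wording. Cross timing (timely, untimely) with pattern (known, none) and alternative cause (none, potential, established): 2 × 2 × 3 = 12 cells. A potential cause is taken as not yet established, and Probable is read as the case where a potential alternative exists. The two clauses of Not related can be combined in three ways: either suffices, the opening clause governs, or both are needed.

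| Cell | Either suffices | Opening clause governs | Both needed | Reworded text |
|---|---|---|---|---|
| Timely, known, none | Definite | Definite | Definite | Definite |
| Timely, known, potential | Probable | Probable | Probable | Probable |
| Timely, known, established | Not related | Not related | no category | Not related |
| Timely, no pattern, none | Possible | Possible | Possible | Possible |
| **Timely, no pattern, potential** | **Not related** | **no category** | **no category** | **Possible** |
| Timely, no pattern, established | Not related | Not related | Not related | Not related |
| Untimely (6 cells) | 6 Not related | 2 Not related, 4 no category | 2 Not related, 4 no category | 6 Not related |
| Cells with no category | 0 | 1 + 4 = 5 | 2 + 4 = 6 | 0 |

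For the cell in bold:

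1. Definite and Probable fail, because both need a known pattern.
2. Possible fails, because a potential alternative cause exists.
3. The opening clause of Not related fails, because no other cause is shown to be definite.
4. The second clause fits if a potential cause counts as one that is present. If it does not, the cell is empty even where either clause suffices (1 empty cell of 12 instead of 0).

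The event is therefore scored as related under 0 of 3 readings. It is Not related under one and has no category under two.

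Followed into SAP 14.3:

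- Scored Not related, it is outside the related table.
- Left blank because nothing fits, it is tabulated at the maximum relationship.

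Two sites could thus place the same event at opposite ends of the scale. The documents do not say whether the case report form accepts a blank score, so that route is an assumption.

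The reworded text gives each of the 12 cells one category and moves 1 cell relative to the either-suffices reading. That result depends on the reading of Probable stated above. If its permissive wording also covers the absence of an alternative, Definite and Probable overlap. If potential also covers established, Probable and Not related overlap. Neither overlap touches the bold cell, and the fix removes neither.

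**The case against.** The strongest reply is that this is untidy wording with little effect. The definitions are guidelines, the second clause of Not related is itself only general, and an investigator may depart from the text. Events with a known pattern still reach Probable when surgery competes as a cause. Some time after the infusion precedes surgery (Protocol 5.7.1.2 has hourly vital signs until it starts). Infusion reactions are tabulated or listed separately (SAP 14.4). All AEs through Visit 4 are recorded (Protocol 7.2.1), all TEAEs stay in the overall tables and listings, and no hypothesis test uses the related subset. These points stand and limit the size. They do not supply a related category for this event, and leaving the matter to judgement invites sites to differ.

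A reader might infer that such events must be scored Not related, so that the related table is systematically too low. The documents do not support that. Under two of the three readings the event has no category, and a blank score counts as related at the highest level.

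Nor is the conflict with Protocol 7.1 certain. Timing alone, with a competing cause and no pattern, need not be evidence suggesting causation. By the same argument, the rewording may score as Possible some events that would not meet the 7.1 test. That is a real cost.

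**Conclusion.** The defect is on the face of Protocol 7.4 and should be corrected. As written, the related-TEAE table can err in either direction. Under-counting is the more direct result, because Not related is the only category that the event can match.

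The size is unknown. The cell counts describe the wording and say nothing about how often such events occur. The practical importance rests on the assumption that surgery will often be a potential alternative cause.

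It would go too far to infer that events are lost or that expedited reporting fails. Overall TEAE and SAE tables and 24-hour SAE reporting through Visit 4 are not directly affected, and Protocol 7.1 defines a SUSAR by reasonable possibility, not by the 7.4 score. Protocol 5.1.2 names AEs deemed related as those to be monitored, but 7.2.1 still records every AE through Visit 4.

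The effect does reach beyond the table in one respect. AE and SAE reporting after Visit 4 depends on this scale, so a late event still judged timely after the single dose could go unreported. That set is probably small.

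**What to change.** Reword two definitions in Protocol 7.4 and the matching site instructions:

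- **Possibly Related:** timely, no known pattern of response, whether or not a potential alternative cause is present, provided another cause is not established.
- **Not related:** no timely relationship, or evidence that the event is definitely due to another cause. Delete the part reading "the event does not follow a pattern of response and an alternative cause is present".

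Leave Definite, Probable and the SAP 14.3 grouping unchanged. The SAP 14.3 rule for a missing score can also stay, since an event of this kind would no longer lack a category.

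The cost is an amendment to two definitions and a related table that is less favourable and less discriminating, because more perioperative events will be scored Possible. A few more late events may need reporting. The summary by maximum relationship already planned in SAP 14.3 keeps the Definite and Probable counts visible, so a reader can separate them from the added Possible events.
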